## **3. STUDY DESIGN/METHODOLOGY**

### **3.1. STUDY DESIGN**

This is a prospective, randomized, controlled trial, parallel four-arm design, single-center study to compare barbed versus traditional suture closure in revision total knee and total hip arthroplasty.

### **3.2. STUDY INTERVENTIONS & RANDOMIZATION**

#### **3.2.1. STUDY INTERVENTIONS**

### 3.2.1.1. Revision Total Knee

For revision total knee arthroplasty all closures will be performed with knee in approximately 45 degrees of flexion.

#### Group #1:

Traditional closure will consist of arthrotomy (deep layer) closed with figure of eight number 1 vicryl plus followed by closure of the intermediate layer with 0 Vicryl plus. The intermediate layer will be performed at surgeon's discretion especially in thin patients. Subdermal layer with 2-0 vicryl suture followed by subcuticular 3-0 monofilament suture (monocryl PLUS, Ethicon; Johnson & Johnson) and Dermabond advanced. This is considered routine care at NYU Langone Orthopedic Hospital. There is no established protocol for suturing the wound.

#### Group #2:

The barbed suture closure will consist of number 2 Stratafix symmetric PDS PLUS for the arthrotomy, intermediate layer will be performed at surgeon's discretion in thin patients, if performed will entail stratafix spiral, subdermal 2-0 stratafix spiral monocryl plus. Followed by subcuticular 3-0 stratafix spiral monocryl plus suture and Dermabond advance. This is considered routine care at NYU Langone Orthopedic Hospital. There is no established protocol for suturing the wound.

### 3.2.1.2. Revision Total Hip

#### Group #1: Conventional closure

1. The capsule will be closed with Vicryl Plus number 1
2. Deep fascia with figure of eight interrupted number 1 braided absorbable suture (Vicryl plus, Ethicon; Johnson & Johnson, Somerville, NJ)
3. Subdermal fat layer simple interrupted knots using number 2-0 braided absorbable sutures (Vicryl plus)
4. Subcuticular 3-0 monofilament suture (monocryl plus , Ethicon; Johnson & Johnson)
5. followed by the use of skin adhesive (Dermabond Advanced, Ethicon; Johnson & Johnson).

#### Group #2: Barbed suture closure

1. The capsule will be closed with stratafix symmetric PDS Plus
2. Deep fascia will be closed with Stratafix Symmetric PDS Plus (Stratafix symmetric PDS plus, Ethicon; Johnson & Johnson, Somerville, NJ)
3. Subdermal layer with running number 2-0 barbed suture (stratafix symmetric PDS CT-2, Ethicon; Johnson & Johnson, Somerville, NJ)
4. Subcuticular suture with stratafix spiral monocryl plus, Ethicon
5. followed by the use of skin adhesive (Dermabond advanced, Ethicon; Johnson & Johnson).

**Table 2.**

	Active Arm	Control Arm
Capsule	SXPP1A445 (24 inch) Symmetric PDS PLUS- Number 1	Vicryl Plus Number 1

Fascia	SXPP1A445 (24 inch) Symmetric PDS PLUS- Number 1	Vicryl Plus Number 1
Subdermal	SXPP1B414 (27 inch) 2-0 Stratafix Spiral PDS Plus Violet 70cm CT-2	Vicryl Plus 2-0
Subcuticular	SXMP1B104 Stratafix spiral monocryl plus 3-0	Monocryl 3-0
Skin	Dermabond Advanced	Dermabond advanced

All the devices used in this study are 510(k) cleared.

- Stratafix Symmetric PDS Plus Knotless Tissue Control Devices
  - o K182873
- Stratafix Spiral Monocryl Plus Knotless Tissue Control Devices
  - o K182873
- Monocryl Plus Antibacterial Suture
  - o K050845
- Coated Vicryl Plus Antibacterial (Polyglactin 910) Absorbable Suture
  - o K181652

The frequency of using barbed versus conventional sutures for revision total joint (knees and hips) arthroplasty is approximately 75% conventional and 25% barbed at NYU Langone Health.

### 3.2.2.RANDOMIZATION

Once Revision TJA candidates are successfully screened, patients meeting eligibility criteria will be randomized into either the barbed or conventional closure group. After informed consent is obtained and the screening interview is conducted, the principle investigator/sub- investigator or research assistant will electronically randomize a patient to a study group (barbed or conventional closure group) using the REDCap database (web-based secure database application).The NYU Statistics Department will provide the randomization scheme that will be used within the REDCap database to randomly assign patients to one of the two treatment groups. Each patient who qualifies for entry into the study will be assigned a unique study number in chronological order.

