## 12. STATISTICAL ANALYSIS

### Power Analysis

In our analysis if we assume an average length of closure of 30 minutes for revision with standard deviation of 5 minutes in closure time. The study is powered to compare hip and knee revisions separately. With an anticipated average decrease in closure time by five minutes, a minimum of 17 patients need to be included in each group (34 revision hips and 34 revision knees) will need be enrolled (power of 80% [alpha=0.025], one-sided). If we estimate a lost to follow up rate of 15% our recruitment goal will be set at 40 revision knees and 40 revision hips for a total of 80 revision total joints.

To perform our cost analysis, we assume a mean savings of \$200 with a standard deviation of \$50 (14). A minimum of 3 subjects per treatment group will need to be enrolled (power of 80% [one-sided alpha=0.025]). If we estimate a lost to follow up rate of 15%, we will have more than sufficient power with our recruitment goal at 80 enrolled patients, 40 revision TKA and 40 revision THA.

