## **15. DATA SAFETY MONITORING**

No data safety monitoring board will be created for this study. The PI is responsible for data safety monitoring of the study. The PI will review all subject safety data, specifically serious adverse events, adverse events related to bleeding and wound drainage, and infection on a quarterly basis. The predefined endpoints in any of the 4 treatment groups that would result in suspending the study are: 5 or more infections that required re-revision or wound drainage in over 50% of subjects.

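### Section 3.2.2 states no stratification by joint although hips and knees are powered separately, so the barbed/conventional split within each joint is not secured; the power cost is small and the remedy is free

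*Combined protocol and SAP*

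**What the plan says.** - **Allocation.** Section 3.2.2 assigns each consenting patient to the barbed or the conventional group in REDCap. The scheme is to "randomly assign patients to one of the two treatment groups". Its content is left to others: "The NYU Statistics Department will provide the randomization scheme that will be used within the REDCap database". The pre-operative part of section 9 repeats the two-way choice. No section mentions strata, separate lists for hips and knees, block sizes or an allocation ratio.
- **Sizing.** Section 12, Power Analysis: "The study is powered to compare hip and knee revisions separately". It asks for at least 17 per group, that is 34 hips and 34 knees, and recruits 40 of each to allow for 15% loss.
- **Group count.** Section 3.1 describes a "parallel four-arm design". The suspension rule in section 15 applies "in any of the 4 treatment groups".
- **Analysis.** Section 12, Statistical Analysis, compares closures with unpaired t-tests, adds regression to control for surgeon and evaluator, and plans both pooled and by-joint analyses. Joint is not named as a covariate.

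**The concern.** The sample size and the suspension rule are counted in four joint-by-closure cells. The allocation described controls only two groups. The recruitment goal fixes the number of hips and of knees, but not how many of each receive barbed suture. If the list ignores joint, that split is left to chance in exactly the comparisons that the study is powered for.

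Two things could suffer. First, an uneven split lowers the power of a within-joint test below that of an even split of the same total. Second, the closures differ by joint (capsule and deep fascia in the hip; arthrotomy with a discretionary intermediate layer in the knee), so closure time may differ too. In the pooled comparison, a chance difference in the hip/knee mix between arms would then shift the suture contrast in that trial.

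**Working it through.** **Inputs (section 12, Power Analysis).** "anticipated average decrease in closure time by five minutes"; "standard deviation of 5 minutes in closure time"; "power of 80% [alpha=0.025], one-sided". The standardised effect is 5/5 = 1.0. The plan states neither 1:1 allocation nor a randomisation method, so both are assumptions below and two methods are shown.

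**Step 1: reproduce the plan's figures.** The normal approximation gives n per arm = 2 × (1.960 + 0.842)² / 1.0² = 15.70, so 16. For the t-test, power = 1 − F(t₀.₉₇₅,df), where F is the noncentral t distribution with df = n₁ + n₂ − 2 and noncentrality 1.0 / √(1/n₁ + 1/n₂). This gives 0.781 at 16/16 and 0.807 at 17/17. The plan's 17 per arm and 34 per joint are therefore right, and 34 / 0.85 = 40 reproduces the recruitment goal.

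**Step 2: how often an arm has fewer than 17 of 40, before any loss.**
- Coin-flip allocation: X ~ Binomial(40, 0.5), P(17 ≤ X ≤ 23) = 0.732. An arm is short in 1 − 0.732 = 27% of trials for a given joint, and in 1 − 0.732² = 46% for at least one joint.
- List balanced 40/40 over all 80 but ignoring joint: X ~ Hypergeometric(80, 40, 40), P(17 ≤ X ≤ 23) = 0.883. An arm is short in 12% for a given joint. The other joint mirrors it, so the overall figure is also 12%.

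**Step 3: what an uneven split does to power.**

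| Split of 40 | Power | Split of 34 | Power |
|---|---|---|---|
| 20/20 | 0.869 | 17/17 | 0.807 |
| 16/24 | 0.855 | 16/18 | 0.806 |
| 14/26 | 0.836 | 15/19 | 0.802 |
| 12/28 | 0.806 | 14/20 | 0.795 |
| | | 13/21 | 0.785 |

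With 40 analysed, power stays at or above 0.80 down to 12/28. With 34 analysed, it does so only down to 15/19.

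**Step 4: average over the chance splits, per joint.**

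| Analysed per joint | Even split | Simple 1:1, mean power | Simple 1:1, P(power ≥ 0.80) | Balanced overall only, mean power |
|---|---|---|---|---|
| 40 | 0.869 | 0.860 | 99.4% | 0.865 |
| 34 | 0.807 | 0.795 | 61% | 0.801 |

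The loss is 0.869 − 0.860 = 0.009 at 40 and 0.807 − 0.795 = 0.012 at 34. Under simple allocation with 34 analysed, power is below 0.80 in 39% of trials, but 14/20 still gives 0.795.

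**Step 5: what stratification would secure.** With 1:1 blocks of 4 within joint (an illustration), 40 per joint gives 20/20. If only 34 are randomised, the split is 17/17 or at worst 16/18. It does not guarantee 17 after losses. If each patient is lost independently with probability 15%, both arms of a joint keep 17 or more in about 42% of trials starting from 20/20, against about 19% under simple allocation.

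**Step 6: the pooled contrast.** If mean closure time differs between joints by D minutes and the proportion of hips differs between arms by d, the unadjusted contrast shifts by d × D in that trial. For example, hips split 24/16 and knees 16/24 give d = 24/40 − 16/40 = 0.20. The plan gives no D; it uses one mean of 30 minutes and one SD of 5 for both joints. For assumed D of 2, 5 and 10 minutes, the shift is 0.4, 1.0 and 2.0 minutes, in either direction and averaging zero over randomisations.

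**The case against.** The strongest reply is that silence is not absence. The statistics department supplies the scheme, and it may already be stratified. Assigning a patient to one of two groups fits a stratified scheme, because the joint is known before randomisation. Section 3.2.1 defines a Group 1 and a Group 2 separately for knees and for hips, which fits a count of four. All of this stands. A reader might infer that the trial is randomised without stratification, or that two groups and four arms are rival designs. The documents support neither; they show that stratification is not stated and that the labels are loose.

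A second reply is that falling below 17 is the wrong yardstick. This also stands. Seventeen is the minimum for an even split of 34. With 40 analysed, 16/24 and 14/26 give more power than 17/17, and 12/28 gives practically the same. A reader might take the 27% or 46% as the chance of an underpowered comparison. It is not, and both figures also assume coin-flip allocation.

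Third, closure time is recorded at surgery (section 9, perioperative data), so loss to follow-up does not by itself remove the primary endpoint, and 34 analysed is close to the worst case planned for. This stands in part: section 5.1 withdraws patients for missed visits or deviation from the closure protocol, and the plan does not say whether their closure times are kept.

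Fourth, a chance hip/knee imbalance adds variance to the pooled contrast, not systematic bias, and it cannot affect the by-joint analyses. That is correct. It still leaves a reason to adjust the pooled analysis for joint, since the planned regression names only surgeon and evaluator.

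**Conclusion.** The point holds as a modest gap in the design as described. The sizing needs a controlled split within each joint, and section 3.2.2 states nothing that provides one. It does not show that the sample size is wrong, since 17, 34 and 40 all reproduce.

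The size is about one power point per joint, under the plan's own 5-minute difference and SD and an assumed simple 1:1 allocation. It is smaller if the list is balanced overall. Only if analysed numbers fall to about 34 per joint does chance imbalance often take power below 0.80, and then usually by little. The pooled effect cannot be sized from the documents because no hip–knee difference is given.

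The change is worth making because it costs nothing and matches the allocation to the comparisons that were powered.

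**What to change.** 1. **Section 3.2.2:** state 1:1 permuted-block allocation stratified by joint (hip/knee) in REDCap, with 40 per joint as section 12 already plans. Randomly varying block sizes would make the next assignment harder to predict. If the statistics department's scheme is already of this form, one sentence is enough.
2. **Section 12:** include joint as a covariate in the pooled closure-time analysis. This removes between-joint variance and any remaining chance imbalance. It is needed even with stratified allocation, because an unadjusted pooled t-test would leave the between-joint variance in the error term.
3. **Sections 3.1 and 15:** align the four-arm and four-group wording with two randomised closures within each of two joint strata.

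Cost: a different allocation table in REDCap, one model term and a few sentences. No extra patients, visits or staff. This is a free improvement.

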## 4. STUDY POPULATION

The study population will include patients undergoing revision total joint arthroplasty by surgeons from NYU Langone Health. All patients who present for evaluation for revision total joint arthroplasty will be screened to determine their study eligibility. Only patients who meet inclusion criteria based on the study screening protocol will be eligible for study participation.

### 4.1. INCLUSION CRITERIA

1. Patients  $\geq$  18 years of age

2. Surgical candidates undergoing revision total knee or total hip arthroplasty for one of the following indications second stage of two stage reimplantation for infection, mechanical loosening, instability, polyethylene wear, stiffness, or periprosthetic fracture

#### **4.2 EXCLUSION CRITERIA**

1. Patient is  $\leq$  18 years of age
2. Patient is unable to provide written consent
3. Patient has active infections in the operative leg/joint
4. Known Allergy to Suture material
5. Underlying Dermatological diseases affecting surgical site including dermatitis, eczema, or psoriasis; connective tissue or vascular disorders or diseases that would adversely affect wound healing; metastatic cancer; renal insufficiency (dialysis); steroid dependence; malnourishment; and other disease processes resulting in an immunocompromised state. Diabetes, smoking and obesity will be allowed as they are frequent comorbidities in our revision joint population
6. Anterior total hip replacement
7. Stage 1 of two stage revision for infection
8. Closure performed by plastic surgeon, including flap coverage

Vulnerable populations will not be enrolled in this study.

#### **5.1 Withdrawal Criteria**

1. Failure to attend regularly scheduled follow up appointments
2. Deviation from closure protocol

### **9. STUDY PROCEDURES/DATA COLLECTION**

#### **a. SCREENING STUDY PROCEDURES**

Subjects will be recruited by prescreening participating surgeons' clinic and surgical schedules. Prior to consenting, research personnel will evaluate all patients to determine if subjects meet the inclusion and exclusion criteria. Participants will continue the use of all medications deemed necessary by their medical doctor during the study period. All patients eligible for enrollment will be asked to sign a consent form prior to beginning the study by a study team member (sub-investigator, research coordinator, etc.).

#### **b. INFORMED CONSENT**

Written informed consent will be obtained from all subjects before any study related procedures are performed. The investigator(s) has both ethical and legal responsibility to ensure that each subject under consideration for enrollment is given a full explanation of the study. This process must be documented on a written Informed Consent Form (ICF) that has already been reviewed and approved by the same Institutional Review Board and/or Independent Ethics Committee (IRB/IEC) responsible for approval of the protocol. Each ICF shall include the elements required by Food and Drug Administration (FDA) regulations in 21 (CFR) Part 50 and International Committee on Harmonization (ICH) Good Clinical Practice (GCP).

Once the investigator or designated research personnel have fully explained the study and answered all the potential questions the participant may have and it is agreed that the participant understands the implications of participating, the IRB approved informed consent form should be signed and dated by all applicable parties in accordance to the IRB/IEC requirements. Study team should give a copy of the signed consent form to the participant and the original should be kept in study subject binder or regulatory binder. Explanation of study and the signing of the informed consent must occur prior to the subject's participation in the trial.

If the patient meets the study entry criteria, the study will be introduced to them by study personnel. A thorough explanation of the study will be provided to the patient and sufficient time will be provided for the potential subjects to thoroughly read the consent form, ask and have all questions about study participation answered,

and make an informed decision to participate. The prospective participants will be encouraged to discuss the study and their potential participation in the study with their family members or significant others. The patient must be able to read the consent form in order to participate in the study. The patient will either provide a written signature to signify their agreement to participate in the study or they will decline study participation. In cases in which the patient decides not to participate in the study, they will be provided with the standard of care at the institution for their surgical procedure.

During the informed consent process, potential study participants will be informed that they may discontinue study participation at any time. If a study participant chooses to withdraw from the study, they will be asked to notify the principal investigator or a member of the study staff of their intentions.

Potential study participants also will be told that the principal investigator may choose to withdraw a study participant from the study for reasons related to noncompliance with the study protocol or if an event occurs that would warrant this decision. In such cases, the principal investigator will provide an explanation for the decision and the reason why the decision was made. Specific data forms will be completed to document the reasons for study participant withdrawal from the study.

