#### *Secondary Endpoints*

1. Record all complications (including needle sticks and glove perforations) and infections related to the wound closure
2. Calculate the cost difference based on supplies, personnel, and OR time between each technique
3. Gather pictures of wound following closure to evaluate the cosmetic result of barbed versus traditional suture in revision total joint arthroplasty using the Patient and Observer Scar Assessment Scale (POSAS)
4. Calculate the number of suture used and length of incision for each technique

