### Data Collection

After the patient has enrolled in this study, data will be directly collected from the patient and supplemented with electronic medical record (EMR) chart review. Additional data may be extracted from clinical notes. All members of the team will be trained in the reproducibly collection of clinical data. All data will then be input into REDcap. A member of the research team will be present at each patient follow-up to ensure that all necessary data points are collected. In addition, the research team may assist the physician when measuring the patient's functional outcomes.

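### Withdrawal grounds differ between sections 5.1 and 9.b, and complications after withdrawal have no stated route into the 90-day rates or the suspension count

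*Combined protocol and SAP*

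**What the plan says.** **Grounds for withdrawal.** Section 5.1 of the protocol gives two: "Failure to attend regularly scheduled follow up appointments" and "Deviation from closure protocol". Section 9.b (Informed Consent) says patients will be told that the principal investigator may withdraw them "for reasons related to noncompliance with the study protocol" "or if an event occurs that would warrant this decision". No section defines the event.

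**What follows withdrawal.** Section 9.b adds: "Specific data forms will be completed to document the reasons for study participant withdrawal from the study". No section says whether a withdrawn patient's data are kept, whether follow-up continues, or whether the patient stays in a denominator. The statistical analysis text in section 12 defines no analysis population.

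**Outcomes concerned.** The first secondary endpoint in section 2.3 is to "Record all complications (including needle sticks and glove perforations) and infections related to the wound closure". Section 15 suspends the study if any of the four groups has "5 or more infections that required re-revision or wound drainage in over 50% of subjects". The principal investigator is responsible for safety monitoring, and there is no monitoring board.

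**Data source.** Under Data Collection in section 11, after enrolment "data will be directly collected from the patient and supplemented with electronic medical record (EMR) chart review".

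**The concern.** The intervention is a single wound closure, finished in the operating room. No post-operative event can call for stopping it, so withdrawal after surgery can only end observation. The events most likely to be thought serious enough (drainage, dehiscence, infection, reoperation) are the ones the secondary safety endpoint is meant to measure. The missed-visit criterion in section 5.1 raises the same problem: a patient who is absent because a complication is being treated elsewhere meets it.

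The person who may withdraw a patient is also the only safety monitor. The protocol describes no blinding, and section 3.2.2 allows the principal investigator to carry out the randomization.

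Two things are at stake: the objective in section 2.1 of faster closure without more wound complications, and the only suspension rule in the plan. If follow-up stops selectively in patients whose wounds are doing badly, the 90-day rates and the counts behind the rule will be too low.

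**Working it through.** **1. Do the two lists match?** Closure deviation and missed visits can both be read as noncompliance, although section 9.b is worded more broadly. The event ground has no counterpart in section 5.1.

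**2. What can post-operative withdrawal stop?** Closure time, incision length, suture count and needle or glove incidents are collected perioperatively (section 9.d). What remains is complications, re-revisions, antibiotic use, the scar image and the scar score. Only these can be lost.

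**3. Follow one patient through the plan.** Suppose a patient has wound drainage and is withdrawn.
- The drainage can be recorded. It falls under the first secondary endpoint, wound problems in hospital are charted as routine care (section 9.e), the withdrawal form gives the reason, and section 15 has the principal investigator review all safety data.
- Suppose the same patient then has an infection that is re-revised before day 90. Section 11 does not say that chart review continues after withdrawal, section 12 does not say whether the patient is analysed, and section 15 does not say whether the patient is counted. The later event has no stated route into the data.

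**4. How does the plan treat lost patients elsewhere?** Section 12 assumes a 5-minute difference, SD 5 minutes, one-sided alpha 0.025 and 80% power. The two-sample t-test calculation gives 16.7, so 17 per group, as stated. Per joint, 2 × 17 = 34, and 34 / (1 − 0.15) = 40, also as stated. Closure time is known before the patient leaves the operating room, so later loss to follow-up cannot remove it. Inflating for that loss makes sense for this endpoint only if lost patients are dropped from the analysis. This suggests exclusion, but it is an inference and not a written rule.

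**5. How sensitive is the suspension rule?** With 40 per joint and equal allocation (assumed, since the ratio is not stated), each group has 40 / 2 = 20 patients.
- Infection limb: 5 qualifying infections with one uncounted leaves 4, below the trigger.
- Drainage limb: 11/20 = 55% meets the rule. One uncounted in the numerator only gives 10/20 = 50%, which is not over 50%. If patients with drainage leave both numerator and denominator, one gives 10/19 = 52.6% (still met) and two give 9/18 = 50% (not met).

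**6. Illustrative range for the infection limb.** The documents give neither an infection rate nor a rate of withdrawal for events, so both are assumed. With X ~ Binomial(20, p(1 − w)), where p is the true risk of an infection needing re-revision and w the share of such infections left uncounted, P(X ≥ 5) is:

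| p | w = 0 | w = 0.2 | w = 0.5 |
|---|---|---|---|
| 10% | 4.3% | 1.8% | 0.3% |
| 20% | 37.0% | 20.6% | 4.3% |
| 30% | 76.2% | 54.4% | 17.0% |

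The table shows what under-counting would do if it happened. It does not estimate how often it would happen.

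**The case against.** The strongest reply is that nothing in the protocol removes a withdrawn patient's data. The endpoint covers all complications, the safety review covers all subjects, and the triggering event is the one least likely to be missed, because it has already occurred and is the stated reason on a form. That stands. A reader might infer that a wound complication itself takes the patient out of the complication endpoint and the suspension count. The documents do not support this. They are silent on retention, and the exposure is to later events.

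A second reply is that the event clause may be meant for something else. Patients are randomized before surgery (sections 3.2.2 and 9.c), and an event before closure could bring a patient under an exclusion in section 4.2, such as active infection in the joint, a first-stage procedure or closure by a plastic surgeon. This is a plausible purpose, and a reason to narrow the clause rather than simply delete it. As worded, though, the clause is not limited to that period.

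A third concerns size. A reader might apply the 15% loss allowance in section 12 to five infections and quote a chance that the trigger is missed. That would not measure this problem. The 15% is a general loss-to-follow-up allowance, the calculation presumes that lost patients' infections go uncounted, and the answer would be the same if the event clause were removed.

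Finally, the consent form was not available for this review and may address data use after withdrawal.

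**Conclusion.** The point holds as an inconsistency and a gap. Sections 5.1 and 9.b do not give the same withdrawal grounds. Withdrawal after closure can end follow-up for outcome-related reasons, and later complications then have no stated place in the 90-day rates or the section 15 counts. Any resulting bias would make complications look rarer than they are.

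Its size is unknown, because the documents give no infection rate, no rate of withdrawal for events and no counting rule. What can be said, assuming 20 per group, is that one uncounted infection, or one or two uncounted patients with drainage, can change whether the rule is met. The drainage case requires that withdrawn patients be left out of the count or that the drainage begin after withdrawal. The point concerns secondary safety outcomes and the suspension rule only. It merits correction because the change is small.

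**What to change.** 1. Reconcile sections 5.1 and 9.b so that they list the same grounds. Limit any event ground to specified events before closure, so that neither a post-operative complication nor a missed visit ends outcome capture.
2. Add to section 5.1 that, unless the patient withdraws consent for data use, wound complications, re-revisions and antibiotic use are still taken from the medical record to day 90 (where section 10 ends data collection), by assigned group.
3. State in sections 12 and 15 that these patients stay in the complication denominators and in the suspension-rule counts. The rule's thresholds need no change for this purpose.

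The cost is a protocol amendment with matching consent wording, and some extra chart review for a few patients using the process already in section 11. Events treated outside the institution may still be missed, so the change reduces the bias without removing it.
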